- b. Potential Risks: There are no known risks of the visual tests and examinations used in this study. There are also no known risks of the visual training to be used. Subjects may become tired during the course of testing and/or training. There is a risk that subject confidentiality will be breached. In addition, as the visual training used in this study is experimental, there may be unknown risks.
- c. Protection against risks: If a subject becomes tired during the course of testing or training, they will be allowed to rest until they feel ready to continue. Subject confidentiality will be protected as well as possible through the use of de-identified ID numbers and secure data transmission.
- d. Benefits: We cannot promise any benefits of taking part in this research. However, possible benefits include an expansion of the subjects' visual fields through the reduction of the cortically blind deficit, and improved visual functioning in portions of the visual field.
- e. Alternatives to participation: Alternatives may include visual training programs or other research studies.

Subject identification, recruitment, and consent/assent

1. Method of subject identification and recruitment: Subjects will be recruited for this study from the clinical practices of the three sites, as well as from waiting lists of subjects who have previously contacted the study sites. If additional subjects are required, we will widen the search to include the clinical practices in the immediate areas near each study site. Examples of the expanded recruitment pool include online hospital recruitment databases such as Iconnect and other forms of digital recruitment. Candidate subjects will then be randomly selected for screening by our inclusion/exclusion criteria. If a subject fails the screening process they will be replaced with a new subject randomly selected from the waiting pool.

2. Process of consent: This study will be conducted in accordance with the provisions of 21 Code of Federal Regulations (CFR) Part 50. In accordance with relevant regulations, an informed consent agreement explaining the procedures and requirements of the study, together with any potential hazards/risks will be read and/or explained to each subject. Each subject will sign such an informed consent form. In this consent, the study will be adequately described in addition to all procedures subjects will need to do, how their confidentiality will be maintained. The subject will be assured of the freedom to withdraw from participation in the study at any time. The consent process for each subject who signs informed consent will be documented in the subject's source (e.g., research file, research progress note) and will include the title of the study, that the consent was discussed with an opportunity for questions and answers, how the subject demonstrated comprehension, that the consent was signed prior to the first study procedure, and that the subject received a signed copy of the consent.
3. Subject capacity: Subjects will only be considered for this study if they are capable of understanding the study, its burdens and risks, their responsibilities, and giving informed consent. Subject capacity will be determined at the time of consent by the person obtaining consent.
4. *Costs to the subject:* There is no cost to participate in this research study except that subjects will be expected to provide their own transportation and/or accommodation to and from the study site for study visits.

Payment for participation: Subjects will receive \$30.00 for each completed study visit. There will be a total of four paid visits. Payment will be received at the end of each visit. This payment may be in the form of a pre-paid debit card, gift card or check at our discretion. Subjects will not be paid for visits that they do not complete. Each subject will be paid up to a total of \$120.00.

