Eye examination: A complete medical history, eye history, and eye examination will be performed in order to determine eligibility for the study. A comprehensive, routine dilated eye exam that includes slit lamp examination and retinal optical coherence tomography (OCT), will be performed on each patient by a qualified ophthalmologist or neuro-ophthalmologist at each site to verify ocular health. OCT should have a signal strength of at least 6, otherwise the test should be repeated. If any problems or signs of ongoing, developing or progressing eye disease are observed, this will constitute grounds for exclusion from the study. The eye examination will include Snellen best corrected acuity, intraocular pressure measurement, exophthalmometry, motility, external examination, slit lamp examination, dilated fundus examination and OCT imaging of the retina.

Visual field testing: Certified technicians will perform 24-2 Humphrey visual fields on each subject. Fixation and pupil monitoring will be “on” for each test. The examination will be performed twice with a 30-minute rest period after each test. Examinations need to be done twice at baseline, with the second test used for future analysis, to ensure that patients are proficient in performing the tests at baseline, so that we can rule out practice on the test as a reason for post-training improvements. During Humphrey perimetry, the eye tracker will be engaged at all times. Tests will be repeated if the patient fails to generate acceptable test reliability (in terms of rate of fixation breaks, false positives and false negatives). If repeated perimetry tests fail to yield acceptable reliability measures (as per device specifications), this will constitute grounds for excluding the subject from the study. Our research to date shows that accurate fixation is critical both to generate reliable perimetry results (our primary outcome measure) and to elicit training-induced improvements in the blind field. All excluded subjects will be replaced with a new enrollment.

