Determination of eligibility: Sites having potential subjects for inclusion into the study will collect the required documentation at the Screening visit and forward relevant medical history, two sets of Visual Fields and an MRI or CT scan of the brain. The medical history will be sent to the Principal Study PI who will, jointly with the Site PIs, review the records for eligibility criteria. The visual fields will be sent to the Visual Field Reading Center for confirmation of visual field defect and reliability/stability of testing. The reading center will forward its information to the Principal Study PI who will jointly determine with the Site PIs whether the subject should appear for a Baseline Visit.

2 - Baseline Visit (Visit BL; 2-4 weeks post SC)

Eye examination: The history and eye examination as described in Visit SC will only be repeated if more than four weeks has elapsed between the Visit SC and Visit BL.

Visual field testing: Humphrey visual field testing as described above will only be repeated if more than four weeks has elapsed between Visit SC and Visit BL.

Eye fixation testing and restoration protocol training: Each subject will undergo MAIA perimetry in order to assess fixation quality and patterns. MAIA testing is a fundus-controlled form of perimetry, and as such, is the most precise way of performing gaze-contingent stimulus presentation. The test output includes a detailed mapping of each patient’s fixation locations during stimulus presentation, allowing us to quantify the spread of their eye movements around the fixation spot.

In addition to performing the MAIA, we will assess the ability to visually process complex visual stimuli in the normal and abnormal portions of the visual field in each subject, using

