Randomization: Eligible subjects will receive their randomization assignment. All subjects will be double masked. Treatment locations and training cohort will be pre-assigned for all subject ID numbers and given to each subject at the end of visit BL. The site will then call the DCBC to obtain the subject ID to be used for each randomized subject and enter this number into the training software, which includes the randomized stimulus sequence.

3 – Post training visit (28 week visit +/- 2 weeks)

Eye fixation testing and restoration protocol testing: The eye fixation testing and protocol testing will be repeated as described for visit BL.

The National Eye Institute Visual Functioning Questionnaire – 25 (VFQ-25) version 2000 and supplement will be repeated, as described for Visit BL.

4 – Post training clinic visit (29 week visit +/-2 weeks)

Eye examination: The history and eye examination will be repeated as described for Visit SC.

Visual field testing: Visual field testing will be repeated as described for Visit SC.

Assessment Schedule

Visit Number	1 (screening)	2 (2-4 weeks post screening)	3 (28 weeks +/- 2 weeks)	4 (29 weeks +/- 2 weeks)
Informed Consent	Y			
Inclusion/Exclusion Criteria	Y			
Demographics	Y			
Medical History	X			X
Concomitant Medications	X			X
Slit-lamp exam	X			X
Retinal Optical Coherence Tomography	X			X
24-2 Humphrey	X			X
24-2 Humphrey repeated	X			X
MRI/CT	Z			
Comprehensive routine dilated eye exam*	X			X
Visual Functioning Questionnaire		Y	Y	
VFQ supplement		Y	Y	
MAIA perimetry		Y	Y	
Eye fixation testing and restoration protocol		Y	Y	

X Performed by clinician

Y Performed by study personnel

Z From patient chart

*dilated fundus exam, Snellen best corrected acuity, intraocular pressure, exophthalmometry, motility, external exam

Unscheduled telephone contacts: These contacts may be initiated by the sites in response to contact from the TC indicating compliance (e.g. missed training sessions) or performance issues (e.g. fixation losses). These contacts may be initiated by the subject for any reason, including equipment failure, motivational issues, or notification of inter-current events that may affect training. The date and reason for the unscheduled telephone contact will be recorded in the source documentation.

Unscheduled visits: These visits may be initiated by the sites in response to contact from the TC indicating compliance (e.g. missed training sessions) or performance issues (e.g. fixation losses).

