These visits may be initiated by the subject for any reason, including equipment failure, motivational issues, or notification of inter-current events that may affect training. The date and reason for the unscheduled visit will be recorded in the source documentation, along with whatever portions of the visit protocol were conducted.

Premature withdrawal: Subjects have the right to withdraw from the study at any time without prejudice. The Site Investigator may withdraw training from a subject in the study in the event of inter-current illness, adverse events, or other reasons concerning the health or well-being of the subject, or in the case of lack of cooperation, non-compliance, protocol violation or other administrative reasons. In the event of premature withdrawal from the study, the Premature Withdrawal (PW) Visit procedures and evaluations should be completed whether or not the withdrawal is determined at a regularly scheduled study visit or at an unscheduled visit. In instances where the subject refuses to return for a PW visit, the Steering Committee may recommend an attempt to obtain outcome data by a visit to a non-participating ophthalmologist. Reasons for withdrawal of the subject prior to completion of the study must be stated in the case report form and in the site source documentation for all study subjects who were enrolled in the study. The DCBC must be informed within 24 hours of all study subjects who are withdrawn due to an adverse event.

Early Discontinuation of Study Training: In the instance that subjects refuse to continue specified training but choose to remain in the study, then scheduled visits should be designated as a NOTRAIN visit and all regular visit activities will be completed.

Re-Entry Visits: In the instance that subjects who opted for Early Discontinuation of Study Training or Premature withdrawal decide to re-enter the study, then a Re-Entry visit with a protocol identical to a Baseline Visit (BV) will be performed, except that the subject's original randomization schedule will be utilized.

Adverse events: An adverse event is any symptom, sign, illness, or experience which develops or worsens during the course of the study, whether or not the event is considered related to the study intervention. A serious adverse event is defined as any adverse medical experience that results in any of the following outcomes:

- death;
- is life-threatening;

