- requires inpatient hospitalization or prolongation of existing hospitalization;
- is a congenital anomaly/birth defect; or
- requires medical or surgical intervention to prevent permanent impairment or damage.

At each subject visit the site study staff will assess adverse events by recording all voluntary complaints of the subject and by assessment of clinical and laboratory features. At each study visit, the subject should be questioned directly regarding the occurrence of any adverse experience since his/her last visit.

All adverse events, whether observed by the Investigator, elicited from or volunteered by the subject, should be documented. Each adverse event will include a brief description of the experience, the date of onset, the date of resolution, the duration and type of experience, the

severity, the relationship to investigational product, contributing factors, and any action taken with respect to the study device. All adverse events occurring between the time of consenting and subject completion or withdrawal from the study will be recorded. Follow up will continue until the adverse event is resolved, including those unresolved at the time of subject concluding study participation.

Data analysis and data monitoring: HVF test results will be analyzed using a custom program in Matlab. Changes in HVF over time will be mapped across the visual field and the area of the visual field that increases or decreases in sensitivity by >6dB will be quantified. Subject age, lesion age, visual deficit size, and type of precipitating neurologic event will be analyzed using linear regression and ANOVA to determine if any of these factors are correlated with change; when appropriate, post-hoc analyses will be conducted using Tukey's HSD and a family-wise Type I error rate of 0.05.

Data storage and confidentiality

- a. Data will be stored on a secure, encrypted server hosted on the URMC private network. Only study personnel directly involved in raw data processing and analysis will have access to data files containing protected health information.
- b. A separate key will be created linking the subject identifiers with a unique study ID number to avoid any direct identifiers stored with the collected data.
- c. Data collected will be used for future research studies.

Risks/benefit assessment

- a. Risk Category: Minimal risk

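### Does the plan leave open which Humphrey field is analysed, at the post-training visit and after repeat tests?

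*Combined protocol and SAP*

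**What the plan says.** Under Methods and procedures, 1 - Screening Visit, Visual field testing, the Humphrey field is done twice in a session, with a rest after each test. The rule for analysis is "Examinations need to be done twice at baseline, with the second test used for future analysis", and the reason given is to keep practice on the test from passing for a training effect. The same paragraph calls perimetry the primary outcome measure and provides for unreliable fields: "Tests will be repeated if the patient fails to generate acceptable test reliability".

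Under 2 - Baseline Visit, a further set is conditional: "Humphrey visual field testing as described above will only be repeated if more than four weeks has elapsed between Visit SC and Visit BL". That visit is planned 2 to 4 weeks after screening.

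Under 4 - Post training clinic visit, the text is one line: "Visual field testing will be repeated as described for Visit SC". The Assessment Schedule has a separate row, "24-2 Humphrey repeated", marked at Visits 1 and 4, so each of those visits has two fields.

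Under Data analysis and data monitoring, fields are compared over time and "the area of the visual field that increases or decreases in sensitivity by >6dB will be quantified". That section does not restate which field enters at either time point.

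**The concern.** Read literally, the second-test rule is worded for baseline and so is its rationale. Visit 4 also yields two fields, it is the only scheduled post-training Humphrey measurement, and nothing there says which field counts. The label can also lose its uniqueness at baseline. A reliability repeat produces a third field, and a late Baseline Visit produces a second set. A subject who returns after stopping has "a Re-Entry visit with a protocol identical to a Baseline Visit (BV) will be performed", which could add one more.

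A related gap concerns Visit 4 fields that stay unreliable after repetition. The screening paragraph treats persistent unreliability as a ground for exclusion and replacement, which would be unsuitable for a randomised subject. Central review is described only at the eligibility stage: "The visual fields will be sent to the Visual Field Reading Center for confirmation of visual field defect and reliability/stability of testing".

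At stake would be the reproducibility of the primary measure. The area beyond a 6 dB cut-off depends on measurement noise, so averaging the two Visit 4 tests, or picking the better one, would give a different area from using the second. An unstated choice could in principle be made after the data are seen.

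**Working it through.** The plan states no power, standard deviation or effect size, so there is no figure to reproduce. The check is mainly a reading of the text.

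**Reading the provisions together**

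1. *Visit 4, ordinary case.* The Visit 4 line refers back to the screening paragraph. That paragraph holds the two-test procedure, the reliability repeat and the second-test rule. The first two clearly carry over, since the schedule shows two tests. Carrying the third over as well is the natural reading, and it compares like with like: second test against second test.
2. *Reliability repeat at baseline.* Inclusion criterion 6 requires at least two reliable fields, and the screening paragraph repeats unreliable ones and excludes subjects whose repeats fail. Analysing a rejected field would defeat that paragraph's purpose. The sensible reading is the second reliable test.
3. *Late Baseline Visit.* Because the planned window is 2 to 4 weeks, a second set arises only when the visit is late. Inclusion criterion 7 then requires repeat fields for randomisation, which points to the newer, pre-randomisation set.
4. *Re-entry.* This follows withdrawal or stopping of training, so it comes after randomisation. Nothing suggests that such a field would serve as the pre-training baseline.
5. *Persistently unreliable Visit 4 fields.* The exclusion and replacement sentences sit under the screening heading. The recruitment section likewise describes replacement of subjects who fail screening, and departures after enrolment have their own Premature withdrawal text. What remains is a missing-data question, separate from which test is the second.

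**Counting candidate pairs (baseline x Visit 4)**

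| Situation | Baseline | Visit 4 | Pairs |
|---|---|---|---|
| No repeats, second-test rule carried to Visit 4 | 1 | 1 | 1 |
| No repeats, rule not carried over | 1 | 2 | 2 |
| Late Baseline Visit and one Visit 4 reliability repeat, rule not carried over | 2 | 3 | 6 |

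**How much the choice could move the measure (illustration)**

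Only the 6 dB cut-off is the plan's. The single-test SD *s* at a location is assumed to be 2, 3 or 4 dB, with independent normal errors and no true change. The chance of a gain above 6 dB at a location is 1 − Φ(6 / SDdiff).

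| Visit 4 field used | SDdiff | s = 2 | s = 3 | s = 4 |
|---|---|---|---|---|
| Second test | s√2 = 2.83, 4.24, 5.66 | 1.7% | 7.9% | 14.4% |
| Mean of the two tests | s√1.5 = 2.45, 3.67, 4.90 | 0.7% | 5.1% | 11.0% |
| Better of the two (simulated) | – | 3.1% | 13.4% | 23.4% |

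Within any row the same figure applies to both cohorts, so with no true change the expected difference between cohorts is zero. These are shares of locations, whereas the plan's measure is a mapped area. They show direction and rough scale only.

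**The case for a change.** The strongest case for a change is that the cross-reference at Visit 4 is being read selectively: it is taken to import the second-test rule but not the exclusion sentence from the same paragraph. The second-test rule also says explicitly that it concerns baseline. Even if the rule carries over, it settles only the ordinary visit and leaves repeats, late sets and unreliable outcome fields to inference. The results are intended for submission to the Food and Drug Administration, and a few sentences would cost nothing in testing.

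Part of this stands. No sentence expressly names the Visit 4 field or says that a Baseline Visit set supersedes the screening set, so the reading above is an inference. The charge of selective reading is weaker. A testing procedure and the choice of test can be repeated at the last visit, whereas exclusion with replacement by a new enrolment is a screening operation that does not fit a subject who has finished training. The better-of-two figures assume a rule that the plan nowhere suggests, and no passage proposes averaging.

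**Conclusion.** This is a gap that analysts fill sensibly. The filler follows from the plan's own provisions: the second reliable test of the session, taken at baseline from the last session before randomisation. The ordinary subject then has one pair of fields, and ambiguity is confined to subjects with repeat sets.

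No bias can be derived from the documents. With one rule for all subjects, applied masked to cohort, the expected between-cohort difference is zero when the cohorts respond alike. If they truly differ, the choice affects the noise and the size of the >6 dB area but does not favour a cohort. That conclusion assumes a common, masked rule. The trial is described as double masked, but the plan does not say separately that field selection is masked.

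Adding text would record a rule; it would not correct a wrong one. A rigid version could do harm: always taking the second Visit 4 test or its last repeat would discard a reliable first test whenever the second stayed unreliable. For fields that stay unreliable throughout, either using them with a flag or treating them as missing is defensible. The plan as written supports a sound comparison, and no change is needed.

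### Does Visit 4, by pointing back to the screening visit, allow randomised subjects to be excluded and replaced on post-training findings?

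*Combined protocol and SAP*

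**What the plan says.** The two exclusion rules and the replacement rule all stand under *1 - Screening Visit (Visit SC)*.

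- *Eye examination*: "If any problems or signs of ongoing, developing or progressing eye disease are observed, this will constitute grounds for exclusion from the study". The same paragraph gives the purpose of the visit's assessment: the "eye examination will be performed in order to determine eligibility for the study".
- *Visual field testing*: unreliable Humphrey fields are repeated. If they remain unreliable, "this will constitute grounds for excluding the subject from the study". The paragraph ends: "All excluded subjects will be replaced with a new enrollment".

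Under *4 – Post training clinic visit*, at 29 weeks, the two instructions are "The history and eye examination will be repeated as described for Visit SC" and "Visual field testing will be repeated as described for Visit SC". Neither limits the reference to how the tests are done.

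Replacement comes up once more, under *Subject identification, recruitment, and consent/assent*: "If a subject fails the screening process they will be replaced with a new subject randomly selected from the waiting pool".

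Departures after enrolment have their own paragraphs, *Premature withdrawal* and *Early Discontinuation of Study Training*. Grounds on which the site investigator may withdraw training include health reasons, "or in the case of lack of cooperation, non-compliance, protocol violation or other administrative reasons".

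**The concern.** The screening paragraph on fields runs procedure and consequence together: repeat, then exclude, then replace. Visit 4 imports that paragraph whole and has no reliability rule of its own. A site that followed the words exactly could exclude a randomised subject at week 29 and enrol another.

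That would matter for two reasons. The trigger would be the reliability of Humphrey perimetry, which the protocol calls its primary outcome measure. The same paragraph also says that accurate fixation is needed both for reliable perimetry and for improvement with training, so exclusion could be related to outcome and might differ by arm. Replacement would then restore 30 per arm and hide the loss. Removing subjects with new eye disease could also conceal a harm. *Data analysis and data monitoring* names no analysis population and no missing-data rule that would override this reading.

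**Working it through.** **1. The passages side by side**

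| Place in the protocol | What it shows |
|---|---|
| Inclusion and exclusion criteria | Exclusion criteria are headed for the screening visit and, additionally, the randomisation visit. None is headed for a later visit. |
| Visit SC, *Determination of eligibility* | Screening ends with a decision on whether the subject goes on to Baseline. |
| Assessment Schedule | Slit lamp, OCT, dilated examination and both Humphrey tests are marked at Visits 1 and 4. The inclusion/exclusion row is marked at Visit 1 only. |
| Recruitment section | Replacement follows failure of screening. |
| Premature withdrawal | Uses a different term and requires a withdrawal visit. If that is refused, outcome data may be sought from an outside ophthalmologist. No replacement is mentioned. |
| Early discontinuation of training | Subjects who stop training but stay in the study complete all scheduled visit activities. |

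**2. Testing the literal reading**

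If repeating as described at an earlier visit imported every sentence of that visit, Visit 4 would determine eligibility for a trial the subject had just finished. Visit 3, which refers back to Baseline in the same way, would choose a first training location after training had ended. The phrase makes sense at both visits only if it means the test procedures. Visit 4 is also the last scheduled visit, and nothing says that data already collected are discarded.

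**3. The harm question**

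*Adverse events* covers any sign or illness that arises or worsens during the study, related or not. All such events are recorded from consent to completion or withdrawal and followed to resolution. Eye disease first seen at Visit 4 is therefore already captured.

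**4. Size, if the literal rule were applied**

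The protocol's own figure reproduces: 3 sites × 20 = 60 and 2 arms × 30 = 60. It gives no effect size, SD, power, dropout rate or week-29 unreliability rate, so everything below rests on assumed rates.

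Let e be the fraction excluded in an arm and d the excluded subjects' shortfall from their arm mean, in SD. With replacement to 30 per arm:

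- Bias = e₁d/(1 − e₁) − e₂d/(1 − e₂)
- SE = √(2/30) = 0.258 SD

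| d | e₂, e₁ | Bias (SD) | Bias/SE | Two-sided error at nominal 5% |
|---|---|---|---|---|
| 0.5 | 5%, 15% | 0.088 − 0.026 = 0.062 | 0.24 | 5.7% |
| 1.0 | 5%, 20% | 0.250 − 0.053 = 0.197 | 0.76 | 11.9% |
| any | equal, same d | 0 | 0 | 5.0% |
| 0 | any | 0 | 0 | 5.0% |

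Either condition alone removes the bias: exclusions unrelated to outcome (d = 0), or equal rates with equal shortfall.

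A second illustration drops the fields of a fraction f in one arm only, with correlation ρ between unreliability and the change score. The shift in that arm's mean is ρφ(z_f)/(1 − f). For ρ from 0 to 0.5 it is 0 to 0.10 SD at f = 10% and 0 to 0.17 SD at f = 20%.

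The cost in precision of losing fields without replacement, at 80% power and two-sided 5%, follows from (1.960 + 0.842) × √(2/n). With 0%, 10% and 20% lost, total N is 60, 54 and 48, and the detectable difference is 0.72, 0.76 and 0.81 SD.

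**The case for a change.** The best argument for the concern is that the cross-reference carries no limit and that the protocol uses similar wording where eligibility does carry over. When Baseline falls more than four weeks after screening, the fields are repeated as described earlier, and reliable repeat fields are then an entry requirement. A site might treat Visit 4 in the same way. The Assessment Schedule is not conclusive either: it leaves the eligibility row blank at Visit 2, although there are additional exclusion criteria at randomisation. The withdrawal grounds end in a broad administrative category. Even on the screening-only reading, nothing says how an unreliable week-29 field is analysed.

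Part of this stands. The wording is loose, and the analysis set and the handling of unreliable Visit 4 fields are unstated. The Baseline parallel does not carry over, because that visit precedes randomisation and a separate inclusion criterion sets the requirement there; Visit 4 has no such criterion. The withdrawal text, however broad, leads to collection of outcome data and not to replacement. The gap at Visit 2 weakens the schedule as evidence, but the section headings, the stated purpose of the examination and the recruitment text point the same way without it.

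**Conclusion.** The concern does not hold as a fault in the plan. Nowhere does the protocol say that randomised subjects are excluded or replaced on post-training findings, and the natural reading of Visit 4 is that the tests are repeated, not the entry decision. The suggestion that new eye disease would be hidden is contradicted by the adverse event rules.

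The bias of 0.06 to 0.20 SD and the error rate of 5.7% to 11.9% need both the literal reading and a three- to four-fold difference in exclusion between arms. The documents support neither. Both arms receive visual discrimination training under double masking, and all subjects meet the same fixation and field-reliability criteria before randomisation. Similar rates with similar shortfall give a bias near zero.

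What is left is missing detail. An analyst would ordinarily fill it by analysing subjects as randomised, flagging unreliable week-29 fields and checking sensitivity to them. Writing that down would record a policy consistent with the existing text, but it would not correct a stated rule or alter the sample size of 60. This conclusion rests on sites reading the screening rules as screening rules, as the headings and the rest of the protocol indicate.

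### The serious adverse event list omits permanent impairment that has occurred, and 24-hour notice depends on withdrawal rather than on seriousness

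*Combined protocol and SAP*

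**What the plan says.** All the relevant text is under Methods and procedures in the combined protocol and SAP.

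- **Definition (Adverse events).** The lead-in is "A serious adverse event is defined as any adverse medical experience that results in any of the following outcomes". Five outcomes follow: death; a threat to life; "requires inpatient hospitalization or prolongation of existing hospitalization"; a congenital anomaly; and an event that "requires medical or surgical intervention to prevent permanent impairment or damage". There is no general item for other important events.
- **Notice (Premature withdrawal).** "The DCBC must be informed within 24 hours of all study subjects who are withdrawn due to an adverse event". This is the only reporting deadline for adverse events in the document.
- **When withdrawal happens (Premature withdrawal).** It is at the investigator's discretion: "The Site Investigator may withdraw training from a subject in the study in the event of inter-current illness, adverse events". Under Early Discontinuation of Study Training, a subject may also stop training and stay in the study. No notice is stated for that route.
- **Recording (Adverse events).** Every adverse event from consent to completion or withdrawal is to be documented, with onset, severity, relationship and action taken. It is then followed until it resolves, even after participation ends.

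**The concern.** There are two separate gaps.

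The first is in the definition. An impairment that was averted by treatment is serious; the same impairment, if it happened and was not treated, is not. The list is inconsistent with itself, and no outside standard is needed to see it. It matters here because every subject already has field loss from a vascular brain injury, so further lasting visual loss is the harm most relevant to them. The risk section also calls the training experimental and allows for unknown risks.

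The second is in the notice rule. The protocol defines serious but attaches no action to it. Prompt notice depends on whether the subject is withdrawn, which is discretionary and is a different question from how grave the event is. At stake is how soon anyone beyond the site learns of a grave event while other subjects continue training.

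**Working it through.** The documents give no figure to reproduce. The check applies the five criteria and the single notice rule, as written, to four types of event.

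| Event | Criteria met (of 5) | Serious? | 24-hour notice? | Documented and followed? |
|---|---|---|---|---|
| A. Treated to avert permanent impairment; subject not withdrawn | at least 1 | yes | no | yes |
| B. Permanent visual loss, no threat to life, no admission, no intervention; not withdrawn | 0 | no | no | yes |
| C. Admission to hospital; not withdrawn | at least 1 | yes | no | yes |
| D. Event meeting no criterion; withdrawn because of it | 0 | no | yes | yes |

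Comparing A with B shows the definition gap: the averted harm is serious and the actual harm is not. Comparing A and C with D shows the notice gap: notice follows withdrawal alone, and two serious events get none while a non-serious one does. The last column is yes throughout.

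Next, which changes are needed:

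- Add the criterion only: B becomes serious, but A, B and C still need no notice.
- Change the notice rule only: A and C gain notice, but B, still non-serious, does not.
- Make both changes: A, B and C all need notice, and D keeps it.

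Finally, how long scheduled visits could leave the site unaware. The inputs are from the visit descriptions and the Assessment Schedule: Baseline is 2 to 4 weeks after Screening, and Visit 3, the first scheduled visit after training starts, is at week 28 ± 2. The document does not say where week 0 lies, so both readings are shown.

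- Weeks counted from Screening: shortest 26 − 4 = 22 weeks, longest 30 − 2 = 28 weeks after Baseline.
- Weeks counted from Baseline: 26 to 30 weeks.

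For an event just after Baseline, the worst case is thus 28 or 30 weeks, or 6.4 to 6.9 months (weeks × 7 / 30.4). Perimetry and the eye examination return only at Visit 4, nominally one week later. This is the delay until the site learns of the event. The further delay until the DCBC is told has no stated limit unless the subject is withdrawn because of it.

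**The case against.** The strongest reply is that nothing is lost. Every adverse event must be documented, with severity and relationship, and followed to resolution. A reader might infer that a permanent loss of vision could go unreported; the documents do not support that. Once known to the site it would be on record whatever its class. What is missing is prompt notice.

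Three further objections have force.

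- The definition gap does not cause the notice gap. Because serious status triggers no action, reclassifying an event would not by itself change who is told or when. This stands, and is why the two gaps are stated separately.
- A reader might infer that counts of serious events by cohort would be too low. No such tabulation or comparison is planned: Data analysis and data monitoring covers perimetry, regression and ANOVA. The inference is not supported.
- The 28 to 30 weeks counts scheduled visits only. Subjects may start an unscheduled call or visit for any reason, and sites may do so when the TC flags missed sessions or fixation losses. These routes can shorten the delay, but they are optional and none requires notice to the DCBC.

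The protocol also rates the study as minimal risk with no known risks of training. That bears on how often such events may occur. It does not supply a rule for handling one.

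**Conclusion.** The point holds in two parts. The list counts a prevented permanent impairment as serious but omits one that has occurred. Separately, the only 24-hour notice is tied to withdrawal due to an adverse event, so a serious event in a subject who is not withdrawn needs no prompt notice. Nor does a lasting visual loss without threat to life, admission, intervention or withdrawal.

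Its size cannot be put in numbers of events, since the documents give no rate and there may be none. The 28 to 30 weeks is a worst case for the site's awareness, not an expected delay. The efficacy analysis is untouched. The conclusion assumes that no separate safety manual or site policy fills the gap; the document refers to none, but cannot show that none exists. The change should be made because it protects subjects at little cost, not because any planned result depends on it.

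**What to change.** Make two changes together under Methods and procedures.

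1. In the Adverse events list, add a criterion: *results in permanent impairment or damage, including clinically confirmed lasting loss of visual field or acuity*. State that confirmation means repeat testing, so that test-retest variation is not counted as a serious event.
2. In the Premature withdrawal notice sentence (or moved to Adverse events), require that the DCBC be informed within 24 hours of the site learning of any serious adverse event, as well as of any withdrawal due to an adverse event.

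The cost is about two lines of text and a few more events classed as serious and reported promptly. One practical point remains for the investigators. Visit 4 already includes a repeated field, but a same-day repeat addresses variability rather than persistence, and no later field test is scheduled. Showing that a loss first seen at Visit 4 is lasting would rely on the existing commitment to follow events until they resolve, and possibly on an added test. The investigators should write down what counts as confirmation. Sample size, endpoint and training are unchanged.
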